## 5. STUDY DRUG ADMINISTRATION AND MANAGEMENT

Study drug will refer to sunitinib and DCC-2618. In cases where there is a distinction in how they are to be administered and managed, details for each will be specified.

### 5.1. Sunitinib

#### 5.1.1. Sunitinib Description

Sunitinib will be supplied as printed hard shell capsules containing sunitinib malate equivalent to 12.5 mg of sunitinib together with mannitol, croscarmellose sodium, povidone (K-25) and magnesium stearate as inactive ingredients.

### 5.2. DCC-2618

[REDACTED]

### 5.3. Study Drug Dose and Administration

Study drug may be dispensed only under the supervision of the Investigator or an authorized designee and only for administration to study patients. Patients will be randomized to receive 150 mg QD of DCC-2618 or 50 mg of sunitinib in repeated 42-day cycles. DCC-2618 will be given continuously and sunitinib will be given continuously for 4 weeks with a 2 week break. Sunitinib dose modifications are allowed per approved package insert or institutional guidelines. Every effort should be made to continue patients receiving sunitinib on a schedule of 4 week on, 2 week off regimen throughout the first cycle, unless toxicity mandates dose modification. PK-guided sunitinib dose escalation is not allowed.

The Investigator or designee must instruct the patient to take DCC-2618 as follows:

- Patients should be instructed to take their assigned dose at the same time each day.
- Patients should take DCC-2618 with a 6-ounce glass of water with or without food.
- Patients must be instructed to swallow the tablets whole. Tablets must not be crushed, chewed, or dissolved in liquid or food.
- The date, amount taken, and time of DCC-2618 administration must be recorded for the 3 days prior to PK sample collections and on the days of PK sample collection.

If a patient forgets to take a dose of DCC-2618 at the scheduled time, the patient can take the scheduled dose if taken within 8 hours of the scheduled time that was missed. If more than 8 hours have passed after the scheduled time, then that missed dose must be omitted, and the patients must continue treatment with the next scheduled dose.

For dosing instructions of sunitinib, refer to the approved package insert or institutional guidelines.

On days of planned study visits, patients will be informed to take the study drug at the study site as per [Table 1](#) (schedule of assessments). The dose of study drug must be administered at the site after pre-dose assessments have been completed. The date, amount taken and time of study drug administration must be recorded in the patient's source documents.

If vomiting occurs immediately after taking a dose, that dose must not be "made up," and the patient may be offered prophylactic anti-emetics prior to their next dose.

For information on overdose, refer to [Section 7.12](#) and the approved package insert or institutional guidelines for sunitinib.

## **5.4. Study Drug Dose Interruption and Modification**

Sunitinib dose interruption and modification will follow guidelines as per the approved package insert or institutional guidelines. PK-guided sunitinib dosing is not allowed. Upon resumption following a dose interruption, the Investigator must continue with the patient's original visit schedule calculated from Cycle 1 Day 1 (i.e. cycle day count is continuous and does not pause with a dose interruption). Clinic visits and assessments should continue during dose interruptions as per [Table 1](#) (schedule of assessments). Dose interruptions of longer than 28 consecutive days will result in the patient being discontinued from the study. If the patient is on 4 weeks on, 2 weeks off cycle, the 28 days is inclusive of the 2 weeks off.

DCC-2618 may be interrupted or modified (i.e. dose reduction) at the discretion of the Investigator at any time due to AE, to accommodate palliative treatment, or for other reasons after consultation with the Sponsor. An interruption must be limited to no more than 28 consecutive days. Upon resumption following a dose interruption, the Investigator must continue with the patient's original visit schedule calculated from Cycle 1 Day 1 (i.e. cycle day count is continuous and does not pause with a dose interruption). Clinic visits and assessments should continue during dose interruptions as per [Table 1](#) (schedule of assessments). Dose interruptions of longer than 28 consecutive days will result in the patient being discontinued from the study.

### **5.4.1. Study Drug Dose Interruption due to Planned Medical Procedures**

Sunitinib should be interrupted for major surgical procedures as per institutional guidelines or the approved package insert.

For DCC-2618, surgeries that occur while the patient is on study, the extent of the procedure and rate of healing following the procedure must be taken into consideration. The following guidance applies:

- Planned minimally invasive surgery: DCC-2618 must be interrupted for 3 days prior to and 3 days after surgery.
- Planned major surgery: DCC-2618 must be interrupted for 5 days prior to and 5 days after surgery.
- Unplanned/emergent surgery: DCC-2618 must be interrupted immediately and restarted as described above for minimally invasive and/or major surgery.

### **5.4.2. DCC-2618 Interruption and Modification Due to Toxicity**

DCC-2618 may be interrupted or reduced as described in [Table 5](#) at the discretion of the Investigator at any time due to AEs and according to the guidelines described in [Table 6](#), [Table 7](#), [Table 8](#), [Table 9](#) and [Table 10](#). Whenever possible, dose reductions should be

prospectively discussed with the Sponsor. If DCC-2618 is interrupted and then DCC-2618 is restarted, the patient should remain on their original cycle schedule.

If any patient requires a dose lower than 50 mg QD or if a patient has had their dose reduced and has disease progression confirmed by the independent radiologic reviewer, the patient must be discontinued from study drug, the End-of-Treatment (EOT) Visit and Safety Follow up Visit must be conducted, and the patient must be followed for OS and PFS2.

**Table 5: Dose Reduction Steps for DCC-2618**

Starting Dose of DCC-2618	1 ST Dose Reduction	2 ND Dose Reduction
150 mg QD	100 mg QD	50 mg QD

If the AE returns to Grade 1 or baseline, the patient should be re-escalated. Efforts must be made to re-escalate the patient to the dose level at which the AE occurred. If the dose level is reduced to the 1st dose reduction level and the AE returns to Grade 1 or baseline, the patient may be re-started at the starting dose level. If a patient has two sequential dose reductions and the AE returns to Grade 1 or baseline at the 2nd dose reduction level, the patient may be re-started at the 1st dose reduction level and must remain at this dose level for 1 cycle without interruption before escalating to the starting dose level.

If the AE leading to dose modification does not return to Grade 1 or baseline within 1 cycle (42 days), then DCC-2618 must be discontinued, unless the event is considered not clinically significant by the Investigator, in which case the possibility of restarting the patient at a reduced dose level may be made after consultation with the Sponsor.

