**Table 7: DCC-2618 Dose Modifications and Management of Hypertension**

Toxicity Grade	Management Guideline*
Grade 1 Prehypertension (systolic BP 120-139 mm Hg or diastolic BP 80-89 mm Hg)	Continue BP monitoring Continue DCC-2618 at the current dose level
Grade 2 Systolic BP 140-159 mm Hg or diastolic BP 90-99 mm Hg Or Symptomatic increase by > 20 mm Hg (diastolic) or to > 140/90 mm Hg if previously within normal limits	Treat BP to achieve diastolic BP $\leq$ 90 mmHg and or systolic BP $\leq$ 140 mmHg 
 
• If BP was previously within normal limits, start antihypertensive monotherapy
 
• If patient is already on antihypertensive medication, titrate dose up
 
 Continue the DCC-2618 at the current dose level Hold DCC-2618 if symptomatic increase by 20 mmHg (diastolic BP) until symptoms resolve and diastolic BP $\leq$ 90 mmHg On resuming DCC-2618, continue at the same dose level
Grade 3 Systolic BP <math>\geq</math> 160 mm Hg or diastolic BP <math>\geq</math> 100 mm Hg Or More than 1 drug or more intensive therapy than previously indicated	Treat to achieve diastolic BP $\leq$ 90 mmHg and or systolic BP $\leq$ 140 mmHg 
 
• Start antihypertensive medication and/or
 
• Increase current antihypertensive medication and/or
 
• Add an additional antihypertensive medication
 
 If symptomatic, hold DCC-2618 until diastolic BP $\leq$ 90 mmHg and/or systolic BP $\leq$ 140 mmHg, and symptoms resolve On resuming DCC-2618, continue at the same dose level If BP is not controlled with addition of a new or more intensive therapy, reduce DCC-2618 by 1 dose level If Grade 3 hypertension recurs despite DCC-2618 dose reduction and antihypertensive therapy, reduce the DCC-2618 by 1 additional dose level
Grade 4 Life-threatening consequences (e.g. malignant hypertension, transient or permanent neurologic deficit, hypertensive crisis)	Treat BP per institutional guidelines Permanently discontinue DCC-2618

BP=blood pressure

\*If BP remains controlled for at least 28 days, DCC-2618 dose re-escalation is permitted at the Investigator's discretion.

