**Table 8: DCC-2618 Dose Modifications for Dermatologic Toxicities (except Alopecia) and Arthralgia/Myalgia**

Toxicity Grade 	Dose Modification Guide
Grade 1	Institute support measures and continue DCC-2618 at the current dose
Grade 2	Institute support measures and continue DCC-2618 at the current dose If no improvement within 7 days, then interrupt DCC-2618 
 
• If the event returns to Grade 1 or baseline within 7 days, resume DCC-2618 at the same dose level
 
• If the event returns to Grade 1 or baseline after 7 days, resume DCC-2618 at a reduced dose level
 
 If this is a recurrence, after event returns to Grade 1 or baseline, resume DCC-2618 at a reduced dose level regardless of time to improvement If after a dose reduction the event is maintained at Grade 1 or baseline for at least 1 cycle (42 days) of dosing, consider re-escalating DCC-2618 by 1 dose level
Grade 3	Institute support measures Interrupt DCC-2618 for at least 7 days or until the event returns to Grade 1 or baseline (maximum 28 days) 
 
• Resume DCC-2618 at a reduced dose level
 
 If after a dose reduction the event is maintained at Grade 1 or baseline for at least 1 cycle (42 days) of dosing, consider re-escalating DCC-2618 by 1 dose level
Grade 4	Discontinue DCC-2618 unless the event is not considered life-threatening. Patients may continue DCC-2618 with non-life threatening events upon discussion with the Sponsor.
Grade: Any	Stevens-Johnson Syndrome / Hypersensitivity Reaction: If a patient experiences Stevens-Johnson syndrome (SJS)/hypersensitivity reaction while being treated with DCC-2618, DCC-2618 must be permanently discontinued. The patient should be immediately referred to a hospital for clinical evaluation and supportive care/management per institutional guidelines. Re-administration of DCC-2618 is not allowed due to the risk of recurrent SJS/hypersensitivity reaction. Caution for recurrence of SJS with other similar agents (TKIs for GIST) is advised.
 The severity of an AE that does not appear in the CTCAE v.5.0 scale must be assessed according to the criteria in Table 12 .	

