**Table 10: DCC-2618 Dose Modifications for Treatment Related Adverse Events Not Mentioned Above**

Toxicity Grade	Management Guideline
Any Grade 3 or 4	Interrupt DCC-2618 dosing until event has resolved to Grade 1 or baseline Once the AE returns to Grade 1 or baseline, reduce DCC-2618 by 1 dose level If a patient tolerates the reduced dose without recurrence of the event for at least 28 days, consider re-escalating the dose of DCC-2618 to the prior dose level
Asymptomatic/Not clinically significant Grade 3 or 4 laboratory AEs (including CPK and lipase) that persist ≤10 days	Closely monitor for clinical symptoms and continue DCC-2618 at the current dose level. Repeat labs within 10 days.
Asymptomatic/Not clinically significant Grade 3 or 4 laboratory AEs (including CPK and lipase) that persist >10 days	Closely monitor for clinical symptoms; for Grade 4 events, interrupt DCC-2618 until the event returns to Grade 3 Asymptomatic Grade 3 or Grade 4 elevations of plasma enzyme: lipase or CPK do not require dose interruption Once the AE returns to Grade 3, resume DCC-2618 at the current dose level or consider reducing by 1 dose level per Investigator discretion after discussion with the Sponsor.
Clinically Significant Grade 3 or 4 laboratory AEs (including CPK and lipase)	Interrupt the DCC-2618. If the Investigator assesses that restarting DCC-2618 is in the patient's best interest, the Sponsor must be contacted for discussion and determination if restarting is allowed.

AE=adverse event; CPK=creatinine phosphokinase

 The rules for dose modifications for laboratory AEs will be based on local laboratory results.

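### Protocol 5.4.2 gives two different instructions for re-escalating ripretinib after a toxicity-related reduction: the text under Table 5 and the event's own table (8, 9 or 10)

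*Protocol*

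**What the plan says.** Protocol 5.4.2 allows ripretinib to be interrupted or reduced along the steps of Table 5 (150, 100, 50 mg once daily), "at the discretion of the Investigator at any time due to AEs and according to the guidelines described in" Tables 6 to 10. It gives no order of precedence.

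The paragraph under Table 5 opens with "If the AE returns to Grade 1 or baseline, the patient should be re-escalated" and continues: "Efforts must be made to re-escalate the patient to the dose level at which the AE occurred". For a patient at the first reduction level whose event has returned to Grade 1 or baseline, it then says "the patient may be re-started at the starting dose level". Its only waiting time applies after two sequential reductions: a patient brought back up to the first reduction level "must remain at this dose level for 1 cycle without interruption before escalating to the starting dose level".

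The toxicity tables use other terms:

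- **Table 8** (dermatologic toxicity, arthralgia, myalgia), after a reduction for Grade 2 or 3: "If after a dose reduction the event is maintained at Grade 1 or baseline for at least 1 cycle (42 days) of dosing", the site is to consider going up one level.
- **Table 9** (isolated bilirubin), Grade 3 or 4: resume at 100 mg on recovery, and consider re-escalation once that dose has been tolerated without recurrence for at least 28 days.
- **Table 10** (other treatment-related events), Grade 3 or 4: reduce one level on recovery; then "If a patient tolerates the reduced dose without recurrence of the event for at least 28 days, consider re-escalating the dose of DCC-2618". The target is the level held before the reduction.

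The SAP contains no dose-modification rule that settles the matter.

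**The concern.** A site with a patient on 100 mg whose event has settled finds two texts that both apply. One says the patient should go back up, with efforts required and no period to wait. The other says to think about it after four or six weeks without a return of the event. A site that follows either text exactly departs from the other.

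What is at stake is when a patient is re-exposed to the dose at which the toxicity occurred. Three analysis items also depend on it: the count of patients with at least one dose increase or reduction and the relative dose intensity (SAP 9.1 and 9.1.1), and the classification of protocol deviations (SAP 6), which needs one standard to judge against. The problem sits in the ripretinib arm only, because sunitinib modification follows the package insert or institutional guidelines (Protocol 5.4).

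**Working it through.** The plan states no figure to reproduce, so the first step is a comparison of texts.

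| Text | Situation | Dose on return to Grade 1 or baseline | Strength of re-escalation wording | Minimum time first |
|---|---|---|---|---|
| Under Table 5, sentences 1 and 2 | Any adverse event | Re-escalate toward the level at which it occurred | *should*, *must* | None stated |
| Under Table 5, sentence 3 | After one reduction | Starting dose | *may* | None stated |
| Under Table 5, sentence 4 | After two reductions | First reduction level, then starting dose | *may*, then *must* remain | None for the first step; 1 cycle for the second |
| Table 8 | Grade 3, or Grade 2 that recurs or returns after 7 days | Reduced level | *consider* | 42 days |
| Table 9 | Grade 3/4 bilirubin | 100 mg | *consider* | 28 days |
| Table 10 | Grade 3/4 treatment-related | One level lower | *consider* | 28 days |

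**Rows outside the conflict.**

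- Table 6 is permanent discontinuation.
- Table 7 depends on blood-pressure control, not on return to Grade 1: "If BP remains controlled for at least 28 days, DCC-2618 dose re-escalation is permitted at the Investigator's discretion".
- A first Grade 2 event in Table 8 that returns within 7 days of interruption resumes at the same dose.
- Table 9 Grade 2 resumes at 100 mg and has no re-escalation rule of its own.
- In Table 10, the row for asymptomatic laboratory events lasting more than 10 days uses return to Grade 3 as its trigger.

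**Does reading the texts in sequence remove the conflict?** Suppose the Table 5 paragraph is the later step, for a patient already reduced. Reducing first and re-escalating later are then compatible. What remains is the later step itself: *should* and *must* with no wait after one reduction, against *consider* after at least 28 or 42 days. The Table 5 paragraph is also mixed within itself, since its third sentence makes optional what its first two direct. After two reductions it sets no wait for the step from 50 to 100 mg, where Table 8 asks for 42 days before any one-level increase.

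**Size for one patient.** SAP 9.1.1 defines relative dose intensity for a cycle as cumulative dose divided by (days in cycle × 150 mg). A full 42-day cycle is 42 × 150 = 6,300 mg. Compare a patient held at 100 mg for the table's minimum period with one returned to 150 mg at once:

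- 28 days (Tables 9 and 10): 28 × (150 − 100) = 1,400 mg; 1,400 / 6,300 = 22.2 percentage points.
- 42 days (Table 8): 42 × 50 = 2,100 mg; 2,100 / 6,300 = 33.3 percentage points.

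These figures assume a single reduction from 150 to 100 mg, the whole waiting period inside one cycle, daily dosing, and re-escalation on the first day the table allows. Over a longer treatment the effect on overall relative dose intensity is diluted. If the site considers re-escalation and declines, the gap continues.

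**The case against.** The best defence is that the Table 5 paragraph gives the dose ladder and the general aim, while the specific table gives the timing. Section 5.4.2 points to Tables 6 to 10 as guidelines, leaves room for investigator discretion, and asks for dose reductions to be discussed with the sponsor where possible. This is a sensible reading, and many sites would probably adopt it. But the protocol does not say that the specific table governs, and the sentence granting discretion concerns interrupting or reducing, not re-escalating.

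The defence does defeat several stronger readings that a reader might infer:

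- *That one event faces competing waits of 0, 28 and 42 days.* Tables 7 to 10 cover different toxicities, so an event falls under one table and meets two instructions at most. A wait of zero is written nowhere; the Table 5 text is silent after a first reduction.
- *That sites are told to reduce and to re-escalate at the same moment.* The sequential reading removes this.
- *That all the toxicity tables conflict with the Table 5 text.* Tables 6 and 7 and the exempt rows listed above do not.
- *That recurrent-event results would be distorted.* SAP 9.2 counts patients, once per term at worst severity in the severity tables, and plans no recurrent-event analysis.

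The number of patients affected may also be modest. In Protocol Table 3 (Phase 1, 150 mg once daily, n=114, terms in at least 10% of patients), hand-foot syndrome had 4 Grade 2 and 1 Grade 3 cases, myalgia 6 Grade 2, and rash, arthralgia and dry skin 1 Grade 2 each. That is 5 + 6 + 1 + 1 + 1 = 14 patient-terms, at most 14/114 = 12.3% of patients if none overlap, and only some would reach the conflicting rows. Lipase had the most Grade 3-4 cases (9 + 2 = 11), but asymptomatic elevations do not require interruption under Table 10. Rarer terms are not in Table 3, so this is indicative only.

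**Conclusion.** The inconsistency is real but narrow. It lies between the paragraph under Table 5 and Tables 8 (the rows named above), 9 (Grade 3/4) and 10 (Grade 3/4 treatment-related events), and concerns the strength and timing of re-escalation for a patient already on a reduced dose. The difference is *should* or *must* with no stated wait after a first reduction, against *consider* after at least 42, 28 and 28 days. For one patient and one episode this is up to 33.3 percentage points of relative dose intensity in a cycle under Table 8 and 22.2 under Tables 9 and 10, on the assumptions stated. How many patients will meet it cannot be determined from the documents.

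The consequences are for patient safety through the timing of re-exposure, for exposure summaries and for deviation classification. A reader might infer a threat to the primary result; the documents do not support that, because no PFS, ORR or OS calculation depends on the re-escalation rule. It should be corrected as a wording inconsistency with safety relevance.

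**What to change.** Reconcile Section 5.4.2 and the paragraph under Table 5 with Tables 8, 9 and 10, so that each toxicity carries one trigger, one minimum period and one strength of instruction for re-escalation. State explicitly which text governs where the general paragraph and a table differ. The same edit should settle the mixture of *should*, *must* and *may* under Table 5. Which rule is clinically right is for the sponsor's clinical team; none is proposed here.

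If patients have already been reduced under the present wording, the document that pre-specifies important deviations (SAP 4.4) should record which text served as the standard before and after the change.

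The cost is a protocol wording amendment, with the approvals that Protocol 11.2 requires, and notification of sites. Sample size, event targets, alpha and the efficacy analyses are untouched.

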**Table 6: DCC-2618 Dose Modifications for Left Ventricular Systolic Dysfunction**

Toxicity Grade	Management Guideline
Any Grade 3 or 4	Permanently discontinue DCC-2618

**Table 7: DCC-2618 Dose Modifications and Management of Hypertension**

Toxicity Grade	Management Guideline*
Grade 1 Prehypertension (systolic BP 120-139 mm Hg or diastolic BP 80-89 mm Hg)	Continue BP monitoring Continue DCC-2618 at the current dose level
Grade 2 Systolic BP 140-159 mm Hg or diastolic BP 90-99 mm Hg Or Symptomatic increase by > 20 mm Hg (diastolic) or to > 140/90 mm Hg if previously within normal limits	Treat BP to achieve diastolic BP $\leq$ 90 mmHg and or systolic BP $\leq$ 140 mmHg 
 
• If BP was previously within normal limits, start antihypertensive monotherapy
 
• If patient is already on antihypertensive medication, titrate dose up
 
 Continue the DCC-2618 at the current dose level Hold DCC-2618 if symptomatic increase by 20 mmHg (diastolic BP) until symptoms resolve and diastolic BP $\leq$ 90 mmHg On resuming DCC-2618, continue at the same dose level
Grade 3 Systolic BP <math>\geq</math> 160 mm Hg or diastolic BP <math>\geq</math> 100 mm Hg Or More than 1 drug or more intensive therapy than previously indicated	Treat to achieve diastolic BP $\leq$ 90 mmHg and or systolic BP $\leq$ 140 mmHg 
 
• Start antihypertensive medication and/or
 
• Increase current antihypertensive medication and/or
 
• Add an additional antihypertensive medication
 
 If symptomatic, hold DCC-2618 until diastolic BP $\leq$ 90 mmHg and/or systolic BP $\leq$ 140 mmHg, and symptoms resolve On resuming DCC-2618, continue at the same dose level If BP is not controlled with addition of a new or more intensive therapy, reduce DCC-2618 by 1 dose level If Grade 3 hypertension recurs despite DCC-2618 dose reduction and antihypertensive therapy, reduce the DCC-2618 by 1 additional dose level
Grade 4 Life-threatening consequences (e.g. malignant hypertension, transient or permanent neurologic deficit, hypertensive crisis)	Treat BP per institutional guidelines Permanently discontinue DCC-2618

BP=blood pressure

\*If BP remains controlled for at least 28 days, DCC-2618 dose re-escalation is permitted at the Investigator's discretion.

